INVESTIGATIONAL PLAN

Study Title: Cardiogenic SHock Intravascular CooLing TriaL (CHILL-SHOCK)

Principal Investigator: [name]

Co-Investigators:

- [name]
- [name]
- [name]
- [name]
- [name]
- [name]
- [name]
- [name]
- [name]
- [name]
- [name]
- [name] [name], PhD
- [name], APN
- [name]

Sponsor: Investigator initiated with support from ZOLL Circulation, Inc.

Intervention: Therapeutic hypothermia using FDA approved ZOLL Intravascular Temperature Management (IVTMTM) system to achieve core temperature of 32-34° for 24 hours in patients who present with cardiogenic shock.

Manufacturer of Intervention: ZOLL (Chelmsford, MA)

Background

Cardiogenic shock complicates 2-8% of all myocardial infarctions in hospitalized patients and despite advances in revascularization and mechanical support, the mortality rate in these patients can be as high as 50% during the index hospitalization.¹ Cardiogenic shock from alternative causes such as advanced heart failure, acute myopericarditis, stress-induced cardiomyopathy, and acute valvular regurgitation are also associated with significant morbidity and mortality.

Hypothermia, as defined by 32-34° Celsius, has been proposed as a potential adjunctive therapy in patients with cardiogenic shock. The role of mild hypothermia has been well established in out of hospital cardiac arrests due to ventricular tachycardia or ventricular fibrillation for improved neurological outcome.² In fact, the American Heart Association (AHA) guidelines recommend therapeutic hypothermia (Class I recommendation) with targeted temperature of 32°C to 34°C for 12 to 24 hours in patients who suffer out-of-hospital cardiac arrest due to ventricular fibrillation (VF).³ AHA also recommends induced hypothermia for patients after in hospital cardiac arrest due to any initial rhythm or after out-of-hospital cardiac arrest due to pulseless electric activity or asystole. This is a Class IIb recommendation, compared to Class I for out-of-hospital VF arrest.

The proposed mechanism of improved neurological outcomes with therapeutic hypothermia (TH) likely involves changes in cerebral metabolism.⁴⁻⁶ In addition to neuroprotective effects, hypothermia may improve cardiac performance. Several animal and small human trials have tried to understand the effect of hypothermia on hemodynamics in patients with cardiogenic shock.⁷⁻¹¹ These have showed improved cardiac performance with TH with improved contractility, cardiac output, and reduction in the inflammatory response that accompanies shock. A small trial published in 2012 by Schmidt-Schweda et. al prospectively enrolled 14 patients that were cooled to 33°C and studied their hemodynamics. Interestingly, patients experienced a statistically significant drop in heart rate, but with increased stroke volume, higher mean arterial blood pressure (MAP), and higher cardiac Power index (CPI).¹⁰ All these indices have been associated with improved outcomes in cardiogenic shock.¹³ Most importantly, the Schmidt-Schweda trial established that hypothermia is safe in patients with cardiogenic shock with no severe adverse events experienced in their cohort. There were no complications associated with insertion or removal of cooling catheters and anti-shivering measures were effective even in non-ventilated patients (5 out of 14 patients were breathing spontaneously during therapeutic hypothermia (TH)). While there was a decline in platelets with TH, this did not lead to an increase in bleeding. Another study from authors at the Cleveland Clinic retrospectively evaluated the hemodynamic effects of TH on 14 consecutive patients with cardiogenic shock who underwent therapeutic hypothermia.⁹ The patients who underwent TH had higher cardiac index, lower SVR, and lower vasopressor requirements.⁹ Importantly, TH was deemed safe, and given the positive effects on hemodynamic parameters, the authors proposed that prospective trials are needed to potentially expand the role of TH outside of cardiac arrest.

Patients with cardiogenic shock, regardless of the underlying etiology, present with hypotension, shortness of breath, altered mental status, signs of volume overload (elevated jugular venous pressure, pulmonary rales, lower extremity edema), and evidence of end-organ hypoperfusion. These patients are typically admitted to the Coronary Care Unit (CCU) for aggressive treatment to reverse the course of the disease. Standard of care therapy for these patients involves initiation of ionotropes and/or vasopressors along with diuretics. Often, mechanical circulatory support (i.e. Intra-arterial balloon pump or temporary left-ventricular assist devices) and invasive hemodynamic monitoring (i.e. placement of a pulmonary artery catheter) is necessary.

The results of the small trials mentioned above are encouraging, but larger randomized trials are necessary to establish the role of TH in patients with cardiogenic shock. We propose a first-ever randomized clinical trial to prospectively study the effects of TH in patients with cardiogenic shock. In addition to assessing the safety of TH in this patient population, hemodynamic parameters, echocardiographic assessment of cardiac function during hypothermia, as well electrocardiographic changes with hypothermia will be studied. The echocardiographic changes during TH have never been previously reported. Studying TH in patients with cardiogenic shock is important, as therapies for this highly morbid condition have remained largely unchanged for many years. Given the high mortality associated with cardiogenic shock despite advances in medical and mechanical support, the clinical implications of results from this trial may be large.

Objective

The purpose of the study is to prospectively randomize patients with cardiogenic shock to standard therapy plus therapeutic hypothermia or standard medical therapy alone in order to assess the safety of TH in patients with cardiogenic shock. This study will also help understand the physiologic effects of TH in cardiogenic shock. This will be a pilot study to establish the safety of TH and to assess tolerability of TH in this patient population.

Methods

A. Patient Population:

All patients meeting criteria for cardiogenic shock (defined as systolic blood pressure <90mmHg for at least 30 minutes, Cardiac Index < 2.2 L/min/m², pulmonary capillary wedge pressure (PCWP) ≥ 15mmHg, need for vasopressors, or need for mechanical support to keep systolic blood pressure ≥ 90mmHg) admitted to the University of Chicago Coronary Care Unit (CCU) will be randomized to standard medical therapy or to therapeutic hypothermia (32-34°) for 24 hours plus medical therapy in a non-blinded manner with 1:1 randomization using computer-generated random numbers (simple randomization). The cardiogenic shock may be a result of acute coronary syndromes (STEMI, NSTEMI, or UA), ischemic or non-ischemic cardiomyopathy, myocarditis, hypertrophic cardiomyopathy, stress-induced cardiomyopathy, peripartum cardiomyopathy, or cardiogenic shock in a patient with HF with preserved EF. Patients less than 18 years of age or greater than 89 years of age will be excluded. Patients with

baseline heart rate less than 60 beats per minute, baseline temperatures less than 35°C, recent cardiotomy, history of cardiac transplantation, or those who are pregnant will be excluded.

All patients between the ages of 18 and 89 who meet the criteria for cardiogenic shock in the CCU will be screened. Inclusion and exclusion criteria are listed below.

Inclusion Criteria:

- 1) Cardiogenic shock
 - a) Systolic blood pressure <90mmHg for at least 30 minutes
 - b) Cardiac Index < 2.2 L/min/m²
 - c) Pulmonary capillary wedge pressure (PCWP) ≥ 15mmHg
 - d) Need for central venous access, vasopressors, inotropes and/or mechanical circulatory support (i.e. intra-aortic balloon pump, Impella, ECMO) to maintain systolic blood pressure ≥ 90mmHg
- 2) Etiology of shock
 - a) Acute coronary syndromes (STEMI, NSTEMI, or UA)
 - b) Ischemic or non-ischemic cardiomyopathy
 - c) Myocarditis
 - d) Hypertrophic cardiomyopathy
 - e) Stress-induced cardiomyopathy
 - f) Peripartum cardiomyopathy
 - g) Cardiogenic shock in a patient with HF with preserved EF
- 3) Age ≥ 18 years AND ≤ 89 years
- 4) Admission to the University of Chicago CCU

Exclusion Criteria:

- 1) Baseline heart rate < 60 beats per minute
- 2) Baseline temperatures < 35°C
- 3) Recent cardiotomy
- 4) History of cardiac transplantation
- 5) Current pregnancy
- 6) Contraindication to 9.3 French femoral venous access for placement of intravascular cooling catheter
- 7) Hospice designation (either currently in hospice or previously enrolled within the past 30 days)

B. Data Collected:

The data elements of interest include, but are not limited to the following:

1. *Patient information*
 - a. Name

- b. Date of birth
- c. Medical record number
- d. Phone number
- e. Primary diagnosis
- f. Relevant social and family history
- g. Previous medical history such as clinic notes, current medications, results of all tests, procedures and laboratory assessments.
- h. Medications
- i. Weight and height

2. *Transthoracic echocardiogram (TTE)*
3. *Hemodynamics via pulmonary artery catheter*
 - a. RA pressures
 - b. RV pressures
 - c. PA pressures
 - d. Pulmonary capillary wedge pressure (PCWP)
 - e. Fick cardiac output and cardiac index
 - f. Systemic vascular resistance (SVR)
 - g. Pulmonary vascular resistance (PVR)
 - h. Cardiac power and cardiac power index
 - i. Mixed venous saturation (MVO₂)
4. *Metabolic parameters*
 - a. Serum lactate level
 - b. Basic metabolic panel - Renal function and serum electrolytes
 - c. Hepatic function
 - d. Coagulation parameters
 - e. Complete blood count (CBC)
 - f. Arterial blood gas (ABG)
5. *Physiologic parameters and vital signs*
 - a. Urine output
 - b. Blood pressure
 - c. Heart rate
 - d. Bladder or esophageal temperature
 - e. Respiratory rate
6. *Electrocardiogram*
7. *Vasoactive medication requirements*
 - a. Cumulative inotrope (i.e. milrinone, dobutamine) and vasopressor (i.e. norepinephrine, phenylephrine, dopamine, vasopressin) doses
8. *Blood samples for future research*
 - a. Stored without identifying information for future research, which may include genetic testing

- b. May be shared with outside collaborators for research purposes, with identifiers removed

C. Timing of Data Collection:

Baseline parameters (prior to initiation of cooling):

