5. TTE
6. Blood sample for future research

Endpoints

Primary safety endpoints:

1. Arrhythmia requiring medical therapy or therapy with temporary pacemaker
2. Bleeding requiring transfusions as a direct result of the cooling catheter insertion or secondary to resulting coagulopathy
3. Clinically important bloodstream infection, as confirmed with 2 positive blood cultures, or suspected sepsis in the absence of positive blood cultures with a sequential organ failure assessment (SOFA) score >2
4. Hypokalemia with potassium levels below 3.0mEq/L, not secondary to other identifiable causes

Secondary endpoints:

1. Hemodynamic changes during intervention period – Cardiac output/Cardiac Index, PCWP, SVR, mixed venous oxygen saturation (MVO₂), cardiac power index
2. Cumulative vasopressor and inotrope dose requirements (i.e. number of vasoactive and/or inotropic drugs used)
3. Echocardiographic % change in ejection fraction at 18-24 hours (from baseline)
4. In-hospital all-cause mortality

Procedures

Patients admitted to the Coronary Care unit (CCU) at the University of Chicago will be screened by the study investigators and the cardiology fellow on the CCU rotation. Patients meeting the inclusion criteria, as defined previously, will be identified and randomized after informed consent within 12 hours of presentation. Patients will be randomized to either TH plus standard medical care or to standard medical care alone. A pulmonary artery (PA) catheter will be placed at the bedside or in the Cardiac Cath lab if difficult anatomy is anticipated. As mentioned earlier, placement of a PA catheter is part of the standard of care for management of cardiogenic shock. Currently, patients who are admitted to the University of Chicago CCU with cardiogenic shock routinely undergo placement of PA catheter by the cardiology fellow in the CCU or in the cardiac cath lab. Data from the PA catheter is vital in initiating vasopressors/inotropes, assessing the response to the therapies, and possible need for escalation of therapy (i.e. mechanical support). In this study, patients in each arm will undergo PA catheter placement.

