Laboratory, echocardiographic, and hemodynamic parameters will be obtained for patients prior to randomization, near the end of 24 hour cooling therapy, and after 48-96 hours post-randomization. Core temperature will be measured via either thermal tip at the end of a transurethral urinary catheter or endotracheal temperature probe in intubated patients. Rewarming will be accomplished at 0.3°C per hour until temperature reaches 37°C.

Target Enrollment and Study Duration

In this initial pilot study, we anticipate enrolling 20 patients to the study, 10 randomized to standard medical therapy and 10 patients randomized to standard medical therapy and 24 hours of TH. We anticipate completing enrollment within 6 months.

Statistical Methods

The three-dichotomous primary endpoints will be analyzed using a two-sample independent proportion test or a Fisher's exact test with a Bonferroni method continuity correction for multiple endpoints. Furthermore, numerical secondary endpoints will be presented as either

mean \pm standard deviation or median (interquartile range) based upon the distribution of the data. In addition, all numerical secondary endpoints will be assessed using two independent t tests or Mann-Whitney U test for comparisons. Categorical variables will be tested with chi-square tests of association or Fisher's exact tests. Differences will be considered significant using an alpha value of 0.05 for a two-sided test. Analyses will be performed using STATA MP Version 14 (College Station, TX).

Potential risks and benefits to subjects

A. Benefits:

There is mounting evidence that TH has positive effects on cardiac function. Multiple studies have suggested that TH may offer particular benefit in cardiogenic shock. In this prospective trial, the patients will be randomized to TH or standard medical care using simple randomization. With TH, we expect increased cardiac output, increased contractility, lower SVR, and higher cardiac power index which will lead to improved hemodynamics and potentially decreasing pressor requirements.

B. Risks:

Anticipated adverse events that could possibly occur during the study include, but are not limited to:

1. *Risks associated with TH*
 - a. Shivering
 - b. Arrhythmia
 - c. Coagulopathy with or without clinically significant bleeding
 - d. Hyperglycemia
 - e. Hypothermia
 - f. Electrolyte abnormalities
 - g. Infections
2. *Risks associated with cooling catheter insertion*
 - a. Bleeding
 - b. Infection

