 - c. Vascular injury

Mitigating Risks associated with TH:

Shivering is the most common risk associated with TH. Shivering is a normal physiological response to cooling as it allows the body to expend energy and generate heat. This leads to increasing metabolic demands and subsequent oxygen consumption. Various strategies can be used to combat shivering and have these have been well described in the literature. In patients that are intubated, the most common means of combating shivering is a combination of benzodiazepines, opioid analgesics, and/or neuromuscular blockade.¹⁶ In awake patients, combination of meperidine and warming of skin with air-warming products such a 'Bair Hugger

blanket' (3M, St. Paul, MN) hugger' are utilized.¹⁷ Meperidine is the most beneficial agent to prevent shivering and previous studies have demonstrated significant lowering of the shivering threshold with meperidine.^{17,18} Given that intravascular cooling therapy is common in multiple ICU settings, including the cardiac care unit (CCU), protocols are already in place for the management of shivering, with an institutional-approved anti-shivering protocol often used in patients undergoing TH.¹⁸ In the event of persistent shivering despite therapy with intravenous sedatives, anesthetics (i.e. propofol or meperidine) and/or paralytic agents in intubated patients, the TH protocol will be stopped and patients will be rewarmed to normothermia.

Therapeutic hypothermia may potentially increase the risk of arrhythmias and will be evaluated in this trial. Bradycardia is expected with TH. In the previously published studies, the reduction in heart rate is not significant enough to cause hemodynamic compromise.^{9,17,19} However, if a patient is noted to be persistently bradycardic, with signs or symptoms requiring temporary pacemaker insertion, the TH protocol will be stopped. Bradycardia requiring temporary pacing will be considered an adverse event of cooling if the patient did not have underlying conduction system disease (i.e. first or second degree AV block) prior to cooling. In such cases, patients will be rewarming to normothermia per the rewarming protocol currently in place for intravascular cooling of critically ill patients.

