Appendix 1 – Schedule of Study Activities

	Baseline	18-24 hours (after randomization)	48-96 hours (after randomization)	30-day Follow-Up	90-day Follow-Up
Informed Consent	X				
Review Medial History	X				
Review Medication History	X				
Height and Weight	X				
Vital Signs ^a	X	X	X		
Echocardiogram (TTE)	X	X	X		
Electrocardiogram (ECG)	X	X	X		
Hemodynamics ^b	X	X	X		
Blood Tests ^c	X	X	X		
Vasoactive Medication Dosing		X			
Potassium (pts randomized to cooling)		Q 4 hours			
Glucose Checks (pts randomized to cooling)		Q 1 hour			
Urine Output	X	X	X		
Randomization	X				
Adverse Events		X	X	X ^d	X ^d

^a blood pressure, heart rate, temperature (bladder or esophageal), respiratory rate

^b RA pressures, RV pressures, PA pressures, pulmonary capillary wedge pressure (PCWP), Fick cardiac output and cardiac index, systemic vascular resistance (SVR), pulmonary vascular resistance (PVR), cardiac power and cardiac power index, mixed venous saturation (MVO2)

^c serum lactate level, basic metabolic panel, hepatic function, coagulation parameters, complete blood count (CBC), arterial blood gas (ABG), and optional blood samples for future research

^d to be completed in clinic, when possible, or by phone

^e items to be charged to research during cooling include: meperidine

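### Fick cardiac output is planned without saying whether oxygen consumption is measured or assumed; a fixed normothermic value could bias the 18-24 h flow endpoints towards the effect expected of cooling

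*Combined protocol and SAP*

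**What the plan says.** B. Data Collected, item 3, lists "Fick cardiac output and cardiac index" among the pulmonary artery catheter data. Appendix 1, footnote b, repeats it: "Fick cardiac output and cardiac index, systemic vascular resistance (SVR), pulmonary vascular resistance (PVR), cardiac power and cardiac power index". Mixed venous saturation, a blood count and an arterial blood gas are listed, so the terms for arterial and mixed venous oxygen content are available. Neither list names oxygen consumption, calorimetry or thermodilution. The list in section B is introduced as open: "The data elements of interest include, but are not limited to the following".

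Secondary endpoint 1 is "Hemodynamic changes during intervention period", covering cardiac output/index, PCWP, SVR, mixed venous saturation and cardiac power index. C. Timing of Data Collection places the on-treatment reading 18-24 hours after cooling starts and before rewarming, with a target of 32-34 °C. Statistical Methods compares numerical secondary endpoints by t test or Mann-Whitney test, with no adjustment for temperature or VO2.

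Under A. Benefits the protocol states that with hypothermia "we expect increased cardiac output, increased contractility, lower SVR, and higher cardiac power index". On shivering, the section on mitigating the risks of hypothermia says: "This leads to increasing metabolic demands and subsequent oxygen consumption".

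**The concern.** Fick output is VO2 divided by the arterio-venous oxygen content difference. If VO2 is a fixed value per body surface area, a fall in true VO2 at constant flow narrows that difference, and the formula reports the narrowing as more flow. SVR and cardiac power index are calculated from cardiac output and inherit the error. One arm is deliberately cooled and read while cold, so the error would differ between the arms and would not cancel in the comparison.

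Cardiac output/index, SVR and cardiac power index are three of the five items in secondary endpoint 1 and carry most of the trial's stated physiological aim. A higher output, lower SVR and higher cardiac power index could then appear in the cooled arm because oxygen demand fell, with no change in flow. If neither VO2 nor an independent output is recorded at the cold reading, true flow cannot be recovered later; it can only be bounded.

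**Working it through.** The plan gives no VO2 figure and no power calculation for this endpoint, so there is no figure of its own to reproduce.

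**Inputs from the documents.** Target 32-34 °C (A. Patient Population). Normothermia 37 °C, the rewarming endpoint in Procedures. The drop ΔT is therefore 3 to 5 °C. Ten patients per arm and two-sided alpha 0.05 (Target Enrollment; Statistical Methods).

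**Assumption.** k, the fractional fall in VO2 per °C, is taken as 2-8%, compounding. It comes from no document.

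**Step 1, bias factors.** Let f = 1 − (1 − k)^ΔT be the true fractional fall in VO2.
- Reported CO / true CO = assumed VO2 / true VO2 = 1/(1 − f).
- Cardiac power is proportional to MAP × CO, so its factor is also 1/(1 − f).
- SVR is proportional to (MAP − RA pressure)/CO, so its factor is 1 − f.

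| k per °C | ΔT | 1 − f | CO, CI, cardiac power index | SVR |
|---|---|---|---|---|
| 0% | any | 1.000 | 0% | 0% |
| 2% | 3 °C | 0.98³ = 0.941 | +6% | −6% |
| 2% | 5 °C | 0.98⁵ = 0.904 | +11% | −10% |
| 5% | 3 °C | 0.95³ = 0.857 | +17% | −14% |
| 5% | 5 °C | 0.95⁵ = 0.774 | +29% | −23% |
| 8% | 3 °C | 0.92³ = 0.779 | +28% | −22% |
| 8% | 5 °C | 0.92⁵ = 0.659 | +52% | −34% |

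**Step 2, reversal.** If shivering left net VO2 25% above the assumed value, CO would be multiplied by 1/1.25 = 0.80 (−20%) and SVR by 1.25 (+25%).

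**Step 3, effect on the planned test.** Suppose there is no true effect, mean cardiac index is 2.2 L/min/m² (the entry limit, used only as a reference value) and the SD is 0.4-0.7 (assumed). The spurious difference is d = 2.2 × [1/(1 − f) − 1]. For a t test with n = 10 per arm, the noncentrality is d/(SD × √(2/10)), with 18 degrees of freedom and critical value 2.10.
- f = 10%: d = 0.24, noncentrality 1.37 to 0.78, chance of p < 0.05 about 25% to 11%.
- f = 20%: d = 0.55, noncentrality 3.07 to 1.76, chance about 83% to 38%.

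These figures use the same SD in both arms. Multiplying every cooled-arm reading by 1/(1 − f) also widens that arm's SD. At f = 20% the pooled SD rises by √[(1 + 1.25²)/2] = 1.13, and a simulation with the scaled SD gives about 73% to 31%; at f = 10% it gives about 23% to 11%. All of these exceed the nominal 5%.

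**The case against.** The strongest reply is that no section says VO2 will be assumed. The list in section B is open-ended, so VO2's absence shows that the method is unspecified, not that VO2 will go unmeasured. That stands. The point is therefore conditional, although Appendix 1 repeats the itemised list and again omits the one missing Fick term.

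A second reply is that the documents contain no figure for whole-body VO2 under cooling. Their only relevant statement, on shivering, points the other way. This also stands, and it is why the range must include zero and reversal. It does not remove the problem. The protocol treats shivering with sedation, opioids or paralysis and stops cooling if it persists, so patients still cold at 18-24 h should mostly be those in whom it was controlled. Partial offset would make the error variable rather than absent.

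A reader might go further and infer that output will certainly be overstated, that controls are unaffected, or that the trial cannot answer its physiological question. The documents do not support these readings. The first needs both an assumed VO2 and a net fall. On the second, an assumed VO2 can be wrong in any shock patient, and controls need not be at 37 °C, since only a baseline below 35 °C is excluded; the supportable claim is a differential error. On the third, PCWP, ejection fraction, MAP and heart rate do not use VO2, and the expected rise in contractility is not a Fick quantity.

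**Conclusion.** The concern holds conditionally. The cardiac output method is underspecified at the term most likely to differ between arms. If a fixed normothermic VO2 is used and net VO2 falls, cardiac output/index and cardiac power index at 18-24 h would be overstated by about 6-52% in the cooled arm, and SVR understated by about 6-34%, in the direction the protocol predicts. With ten per arm, that could by itself produce a nominally significant difference. The direction follows from algebra; the size rests on the assumed 2-8% per °C over 3-5 °C. The bias is zero if net VO2 does not fall and reverses if it rises.

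The cooling-related error is confined to the cold reading of a secondary endpoint. The primary safety endpoints, PCWP and ejection fraction are untouched by the Fick calculation. In a 20-patient pilot whose main purpose is safety and tolerability, this should be corrected but is not critical.

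**What to change.** In B. Data Collected, item 3, and in Appendix 1, state whether VO2 is measured or assumed, with the same method in both arms and at all three readings.

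If it is assumed, add to Statistical Methods:
1. A sensitivity analysis that recomputes cardiac output/index, SVR and cardiac power index with VO2 scaled to each patient's recorded core temperature, over a stated range per °C that includes no change. Temperature is already recorded every 1-2 hours in both arms.
2. A rule that a between-arm difference at 18-24 h is described as a flow effect only if it persists across that range.
3. MAP, heart rate and PCWP reported alongside, as quantities that do not depend on VO2. The arterio-venous oxygen difference and mixed venous saturation should not be read as flow measures during cooling, because they carry the same dependence on VO2.

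Thermodilution through the pulmonary artery catheter already planned for every patient is an optional cross-check. It would first have to be checked for interference from the running cooling catheter, which is present in one arm only.

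**Cost.** The assumed-VO2 route needs a few sentences and a little more analysis, with no new data, and the hemodynamic results may look less favourable to hypothermia. Measuring VO2 would remove the bias at source but adds a procedure at each reading.
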